8. RESEARCH QUESTION AND OBJECTIVES

This study asks what are the rates of adverse outcomes of special interest in RA patients treated with tofacitinib in relation to those treated with bDMARD and nbDMARD.

Objectives:

To evaluate the rates of serious infections, malignancy, CV, and other specified outcomes among patients with RA in a Germany-based register who initiate tofacitinib. Rates will also be estimated among existing cohorts of bDMARD and nbDMARDs patients to provide context for rates observed on tofacitinib. No a priori hypotheses will be tested in this descriptive study. Pending feasibility, rates of malignancy, serious infection, CV and other event rates will be compared between tofacitinib-treated RA patients and other comparator cohorts using methods that adjust for sex, age, year of treatment start, treatment history, disease severity, comorbidities, and other potential confounders.

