9.2.1.1. Tofacitinib Exposed Cohort Inclusion Criteria

- 1. Included in RABBIT.
- 2. Initiation of tofacitinib.

9.2.1.2. nbDMARD Cohort Inclusion Criteria

- 1. Included in RABBIT.
- 2. Enrolled after 1 January 2009.
- 3. failure of at least one DMARD and initiation of a new DMARD.
- 4. No previous exposure to bDMARD or targeted synthetic bDMARD (tsDMARD).

9.2.1.3. bDMARD Exposed Cohort Inclusion Criteria

- 1. Included in RABBIT.
- 2. Enrolled after 1 January 2009.
- 3. Initiation of bDMARD therapy.
- 4. No prior exposure to tsDMARD.

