The primary analysis will assume a once exposed always at risk paradigm, as is frequently used in study of malignancy risk due to bDMARDs. 26,14,15,24 Under this approach, follow up for each cohort continues from the cohort index date until the first of a malignancy event, loss to follow up, death or end of study. Follow up for each exposure cohort continues after switching to a new drug or discontinuation of treatment. This approach maximizes follow up time and the ability to capture long latency events, ie, events that occur or are detected years after exposure. Under this approach, events will be double-counted if a patient indexed to bDMARD switches to tofacitinib and a malignancy occurs subsequent to tofacitinib

¹ The potential mechanism for increased PML risk is poorly understood. PML will be evaluated using both on drug and once-exposed always at risk approaches.

exposure. That is, the event will be assigned to both the bDMARD and the tofacitinib exposure cohorts as will the corresponding person years since index to the respective cohorts. Because tofacitinib is expected to be used as a later line therapy, switching is expected to be non-random with most tofacitinib patients having been included in the bDMARD cohort prior to initiation of tofacitinib. In such cases, the bDMARD rate will have more associated person-years and thus a relatively lower rate than the corresponding rate in the tofacitinib cohort.

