Using this primary analytic approach, if neither tofacitinib nor bDMARDs cause an increased risk of malignancy both exposure cohort rates will reflect the background rates of malignancy from the time of index to the end of the study period and the comparative effect measure will indicate no difference in rates. If tofacitinib does cause an increased rate of malignancy, which is the effect we are most interested in detecting, a relatively higher rate will be observed in the tofacitinib exposed cohort. The once exposed always at risk approach is therefore able to detect an increased rate given the non-random switching expected to occur given use of bDMARDs prior to tofacitinib and is consistent with previous studies evaluating the risk of individual biologics. Additional analyses will be conducted to evaluate potential confounders and the impact of different latency assumptions as will be described in the SAP. Sensitivity analyses will be conducted that restrict the bDMARD comparator cohort to patients who were never exposed to tofacitinib or other non-biologic advanced therapies and compare the characteristics of those bDMARD patients ever and never exposed to tofacitinib.

Secondary analyses that censor follow up time after a switch to a different treatment class will also be performed. Among patients indexed to a bDMARD cohort, follow up will begin at index and continue until the first of an event, switch to tofacitinib or other non-biologic advanced systemic therapy, loss to follow up, death, or study end date. Similarly, for tofacitinib, follow up will begin at index and continue until the first of an event, switch to a non-JAK inhibitor-based advanced systemic therapy, loss to follow up, death or study end date. While this approach eliminates the problem of double counting, it may not allow sufficient follow up time to allow for latent effects or detection and decreases the number of events included reducing the statistical power to detect a higher risk of malignancy in tofacitinib treated patients. However, under an assumption of no latency or a very short latent period as in an aggressive tumor promoter, this approach would detect an increased risk of disease on tofacitinib relative to the risk due to bDMARDs.

Of note, several studies compared a once-exposed approach to a time on drug and other approaches and found similar rates of malignancy using an on-drug and ever-exposed approach. ^{26,14,15}

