The schematic below provides examples of patterns of event and treatment patterns to illustrate resulting contribution to rate calculation in the once exposed always at risk and censoring at switch analytic models:

- *: bDMARD index date;
- ~: ear on bDMARD;
- ^: tofacitinib index date;
- -: year on tofacitinib;
- O: discontinuation of advanced systemic therapies;
- =: year not on systemic therapy;

X: event.

	Once-exposed always at risk		Censoring at Switch	
Treatment/Event	bDMARD rate	Tofacitinib rate	bDMARD rate	Tofacitinib rate
pattern	contribution	contribution	contribution	contribution
	(events/person	(events/person	(events/person	(events/person
	years)	years)	years)	years)
* ~ ~ ~ ^ X	1/5	1/2	0/3	1/2
* ~ ~ ~ X	1/3	0/0	1/3	0/0
^ O = = = X	0/0	1/6	0/0	1/6 ^a
*~~~ X	1/9	1/6	0/3	0/3
^ ~ ~ X	0/0 ^b	1/7	0/0 ^b	0/4

Patients continue to be followed after index exposure discontinuation if they do not initiate another systemic therapy in a different class.

Note: if an event does not occur, person time will be allocated to rate denominator as described in table without corresponding event.

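### Both specified malignancy analyses keep time and cancers after a switch to another JAK inhibitor in the tofacitinib rate, yet the protocol reads the secondary result as risk on tofacitinib itself

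*Protocol*

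**What the plan says.** The research question in section 8 names one drug: "what are the rates of adverse outcomes of special interest in RA patients treated with tofacitinib", set beside bDMARD and nbDMARD patients.

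Section 9.4 (Risk Window) gives malignancy and NMSC two approaches of their own.

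- **Primary (ever-exposed).** "Follow up for each exposure cohort continues after switching to a new drug or discontinuation of treatment".
- **Secondary (censor at switch).** "Secondary analyses that censor follow up time after a switch to a different treatment class will also be performed". Apart from an event, bDMARD follow-up ends at a "switch to tofacitinib or other non-biologic advanced systemic therapy, loss to follow up, death, or study end date". Tofacitinib follow-up ends at a "switch to a non-JAK inhibitor-based advanced systemic therapy, loss to follow up, death or study end date". A footnote to the schematic repeats the class rule: "Patients continue to be followed after index exposure discontinuation if they do not initiate another systemic therapy in a different class".

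The same section says that, if latency is absent or very short, the secondary analysis would pick up a raised risk on tofacitinib compared with bDMARDs. The one sensitivity analysis it names that restricts a cohort restricts the bDMARD cohort.

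On entry, section 9.2.1.1 asks only for inclusion in RABBIT and "Initiation of tofacitinib". Section 9.2.1.3 adds "No prior exposure to tsDMARD" for the bDMARD cohort, and section 9.2.1.2 bars earlier biologic or targeted synthetic use for the nbDMARD cohort.

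**The concern.** A censor-at-switch analysis is normally read as the one closest to the effect of the index drug. Here it removes later biologic time from the tofacitinib cohort but leaves later JAK-inhibitor time in. Class-level censoring suits the bDMARD cohort, which is defined as a class. The tofacitinib cohort is defined by a single drug, so the same rule gives a rate broader than its label.

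If JAK inhibitors differ in cancer risk, the difference is attributed to tofacitinib. A true tofacitinib signal could be diluted by a safer successor, or a signal could appear because of a riskier one. Neither specified malignancy analysis separates the two.

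The entry rule raises a second, weaker issue. A tofacitinib initiator may have used another tsDMARD before, and for a long-latency endpoint some risk from that exposure may surface after the tofacitinib index date. Neither comparator cohort admits such patients.

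**Working it through.** **Step 1: trace patients through the rules in section 9.4.**

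| Patient | Primary | Secondary |
|---|---|---|
| Tofacitinib, then another JAK inhibitor, then cancer | Counted for tofacitinib | Counted for tofacitinib: the new drug is not a non-JAK therapy |
| Tofacitinib, then a bDMARD, then cancer | Counted for tofacitinib | Censored at the switch |
| bDMARD, then another JAK inhibitor, then cancer | Counted for bDMARD | Censored at the switch |
| bDMARD, then another bDMARD, then cancer | Counted for bDMARD | Counted for bDMARD |

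The first row is the point at issue. The schematic has no symbol for another JAK inhibitor, so none of its examples shows this case.

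**Step 2: entry.** Follow-up in both analyses starts at the tofacitinib index date. A cancer that arose before that date is not counted. Earlier tsDMARD use can therefore act only through risk carried forward.

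**Step 3: illustrate the size.** The protocol gives no rate of switching to another JAK inhibitor, so there is no figure to reproduce. Inputs:

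- Departure from each JAK inhibitor: 30% a year. This is borrowed from Table 2 in section 9.6, where it is the rate of switching from tofacitinib to a bDMARD. Using it for all departures is an assumption.
- Follow-up T = 5 years, the study length in the table titles.
- Share of departures that stay in class, p = 10%, 20% or 30%. Assumed.
- Every departure is treated as a switch. Loss to follow-up is ignored at first.

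Hazard: h = −ln(1 − 0.30) = 0.3567 per year. Mean years under exit hazard x: F(x) = (1 − exp(−xT))/x.

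Years on tofacitinib: F(0.3567) = (1 − 0.1681)/0.3567 = 2.332.

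Only out-of-class departures end follow-up, so the counted years are F((1 − p)h). The share on another JAK inhibitor is 1 − 2.332/F((1 − p)h). If nobody leaves the second JAK inhibitor, the extra years are p × (5 − 2.332).

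| p | Counted years | Share on another JAK inhibitor | Extra years if nobody leaves the second | Share in that case |
|---|---|---|---|---|
| 10% | 2.489 | 6% | 0.267 | 0.267/2.599 = 10% |
| 20% | 2.663 | 12% | 0.534 | 0.534/2.866 = 19% |
| 30% | 2.856 | 18% | 0.800 | 0.800/3.132 = 26% |

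Adding the protocol's 5% annual loss (hazard −ln 0.95 = 0.0513) to both terms of the first version gives 6.0%, 11.8% and 17.5%. Without loss but with T = 7, it gives 8%, 15% and 22%.

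**Step 4: a second parameterisation.** Let within-class switching be its own rate, assumed at 2% to 20% a year, on top of 5% loss and a bDMARD switch rate of 0% (Table 1) or 30% (Table 2). The share is 1 − F(h_loss + h_bDMARD + h_JAK)/F(h_loss + h_bDMARD). The lowest value is 3% (2%, 30% bDMARD switch, 5 years). The highest is 47% (20%, no bDMARD switch, 7 years).

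**Step 5: effect on a rate ratio.** With share s, bDMARD rate 1 and no latency, observed RR = (1 − s) × RR_tofacitinib + s × RR_other.

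- RR_tofacitinib = 2 and RR_other = 1: s of 6%, 12% and 18% gives 1.94, 1.88 and 1.82. Over the Step 4 range it runs from 1.97 to 1.53.
- RR_tofacitinib = 1 and RR_other = 2: the same s gives 1.06, 1.12 and 1.18. Over the Step 4 range it runs from 1.03 to 1.47.

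**The case against.** The class rule is deliberate. The protocol announces it, repeats it in the schematic footnote and applies it in both cohorts: a bDMARD patient who moves to another biologic is not censored either. The stated gain of the secondary analysis is to end double counting, and the rule achieves that. The ever-exposed primary keeps time on every later drug by design, with a latency rationale, and that is not specific to JAK inhibitors. All of this stands, and the class-level version can stay. What remains is that its result is interpreted for a single drug.

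A reader might infer that cancers on an earlier JAK inhibitor also count as tofacitinib events. They do not, because follow-up starts at the tofacitinib index date. A reader might also conclude that 9.2.1.1 should bar earlier tsDMARD use to match the comparators. The documents do not support that: the abstract and section 9.2 define an all-initiator surveillance population, which such a criterion would cut. Treatment history is also a named adjustment variable in sections 8 and 9.8. Adjustment is pending feasibility, however, could address earlier tsDMARD use only in part, and does nothing about events after a later switch. The strata named in 9.8 cover previous biologics, not previous tsDMARDs.

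The SAP might add a suitable run. Section 9.4 defers further work on confounders and latency assumptions to it but fixes the switch-censoring rule itself. The general window that opens 9.4, which stops at discontinuation of the index treatment, does not help, because the section then sets separate approaches for malignancy and NMSC.

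**Conclusion.** The point holds in a limited form. In both specified malignancy/NMSC analyses, time and cancers after a move from tofacitinib to another JAK inhibitor are credited to tofacitinib. The secondary result is therefore risk on tofacitinib or a subsequent JAK inhibitor, not risk on tofacitinib alone. Earlier tsDMARD use is a lesser, separate issue of carried-over latent risk.

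Two stronger readings go too far. The rate is not a JAK-class rate under another name: every patient initiated tofacitinib, users of other JAK inhibitors who never took it are absent, and in the Step 3 illustrations 74% to 94% of counted time is on tofacitinib. Nor can it be said that no planned result would reveal a difference between JAK inhibitors, because the SAP is not shown.

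The size is unknown. About 6% to 18% of person-time follows from the assumed 30% departure rate, 5 years and 10% to 30% of departures staying in class. It is 10% to 26% if nobody leaves the second JAK inhibitor, and 3% to 47% over the wider assumed range of switch rates. The bias can go either way, and its effect depends on a difference between JAK inhibitors on which the documents give no figure.

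**What to change.** - In section 9.4, add a sensitivity version of the secondary malignancy/NMSC analysis that censors tofacitinib follow-up at a switch to any other advanced therapy, including another JAK inhibitor. Keep the class-level version beside it.
- Label the existing version as JAK-class risk after tofacitinib start, and reword the sentence that reads it as risk on tofacitinib.
- Leave the all-initiator criteria in 9.2.1.1 as they are. In any comparative malignancy analysis, add a restriction to, or a stratum of, patients without earlier tsDMARD use.

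The cost is wording and additional runs on treatment data that RABBIT already records (section 9.5.1, item 3). Identifying earlier tsDMARD use needs the same information that the comparator entry criteria already require. The added runs will have fewer person-years and events, so their intervals will be wider. The existing analyses lose nothing.

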9.4. Risk Window

Within each cohort, each patient will be evaluated for safety events of interest while exposed to the index therapy and accrue person-time from the cohort index date until the first occurrence of the event of interest, discontinuation of index treatment, death, loss to follow up, exit from the register or after 7 years of follow up. Interim reports will not censor the existing comparison cohorts to match the tofacitinib cohort on index date or duration of follow up. The final report will censor all patients at 7 years. Follow-up will be uniquely determined for each safety endpoint of interest.

Some outcomes of interest in this study are thought to potentially occur at a higher rate while on drug, but that increased risk subsides after the drug is discontinued (ie, serious infections, herpes zoster, CV events, gastrointestinal (GI) perforation, progressive multifocal leukoencephalopathy (PML). Those events will be evaluated over a risk window that includes time from drug initiation until 90 days after end of treatment. When a patient initiates a new therapy within the 90-day extension, the time and events during the overlapping period will be assigned to both treatments. The 90-day extension period is implemented in part to accommodate ongoing exposure to treatments with longer half-lives, and in part to ensure that any subclinical or undiagnosed illness at time of end of treatment is captured.

For non-melanoma skin cancer (NMSC) and malignancies, the manifestation of which is expected to be delayed relative to the time of exposure, the outcomes will be evaluated using two different approaches, a once exposed always at risk approach as the primary analysis and a censor at switch approach as a secondary analysis. PML rates will also be described using this approach.

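### The malignancy analysis offered for a no-latency effect still counts time after tofacitinib is stopped, so an effect confined to treatment is attenuated, and no on-drug window is specified for malignancy or NMSC

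*Protocol*

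**What the plan says.** All of this is in Protocol section 9.4 (Risk Window).

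- **Two analyses for malignancy and NMSC:** "a once exposed always at risk approach as the primary analysis and a censor at switch approach as a secondary analysis".
- **Primary (ever-exposed):** "Follow up for each exposure cohort continues after switching to a new drug or discontinuation of treatment".
- **Secondary (censor at switch), tofacitinib cohort:** follow-up runs to the first of an event, "switch to a non-JAK inhibitor-based advanced systemic therapy, loss to follow up, death or study end date".
- **Secondary, bDMARD cohort:** follow-up runs to the first of an event, "switch to tofacitinib or other non-biologic advanced systemic therapy, loss to follow up, death, or study end date". Neither secondary list contains discontinuation of the index drug.
- **Note to the schematic:** "Patients continue to be followed after index exposure discontinuation if they do not initiate another systemic therapy in a different class".
- **Purpose given for the secondary analysis:** "under an assumption of no latency or a very short latent period as in an aggressive tumor promoter, this approach would detect an increased risk" on tofacitinib relative to bDMARDs. The same paragraph concedes less follow-up and less power, but does not mention dilution by off-drug time.
- **On-drug window for other outcomes** (serious infections, zoster, CV events, GI perforation, PML): "Those events will be evaluated over a risk window that includes time from drug initiation until 90 days after end of treatment". Malignancy and NMSC are not on that list.
- **PML gets both windows:** "PML will be evaluated using both on drug and once-exposed always at risk approaches".

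**The concern.** If a drug promotes tumours with no latency, the excess exists while the patient takes it and ends when the patient stops. The window that matches this assumption ends at, or shortly after, discontinuation. The secondary analysis does not end there. For a patient who stops tofacitinib and starts nothing in another class, it counts exactly the same time as the primary analysis.

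The off-drug years enter the tofacitinib rate at background risk and lower it. They also come from a selected group, namely those who stop without starting another advanced drug, so cancers arising in that time say little about current exposure.

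What is at stake is interpretation. A secondary rate ratio close to 1 could be read as evidence against a promoter-type effect, because the protocol says this analysis would show one. No other malignancy analysis that the protocol specifies would correct that reading.

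**Working it through.** **1. Reproduce the schematic.** In row 3 the patient starts tofacitinib, stops, spends three years off systemic therapy and then has an event. The protocol credits 1/6 to tofacitinib under both approaches. The on-drug symbols in that row did not survive text extraction, so the on-drug time is inferred as 6 - 3 = 3 years.

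- Stated rule, discontinuation does not censor: 3 on-drug + 3 off-drug = 6 person-years and 1 event, i.e. 1/6. This matches the protocol.
- On-drug window: 0/3, or about 0/3.25 with the 90-day extension.

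The printed 1/6 can only be reached by counting the off-drug years and the off-drug event. The row settles what the rule is.

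**2. Dilution formula.** Let R be the true rate ratio on drug, with no excess off drug, and let f be the off-drug share of counted tofacitinib person-time.

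Observed ratio = R(1 - f) + f = 1 + (R - 1)(1 - f). For R = 2, the two-fold difference used in section 9.6 (Study Size), this is 2 - f.

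**3. Inputs for f.**

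- Loss to follow-up of 5% a year: section 9.6.
- Stopping rate of 30% a year: **assumed**. The 30% in section 9.6 is a rate of switching from tofacitinib to a bDMARD, and those patients are censored at the switch. The figure is borrowed here only as a plausible size.
- Share s of stoppers who start no other class: **assumed** at 10%, 30% and 50%. The protocol gives no figure.
- Two designs: 7 years with accrual over the first 2 (section 9.6 projects enrolment over 24 months with at least 5 years of follow-up), and 5 years with uniform accrual (titles of Tables 1 and 2).

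**4. Calculation.** Use constant hazards of 0.30 for stopping and 0.05 for loss. For a patient with potential follow-up T:

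- on-drug time = (1 - e^(-0.35T))/0.35
- off-drug time = s × [(1 - e^(-0.05T))/0.05 - (1 - e^(-0.35T))/0.35]

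Averaging over T uniform on 5 to 7 years gives 2.50 on-drug years and 2.68 × s off-drug years. Averaging over T uniform on 0 to 5 years gives 1.51 and 0.80 × s. Then f = off/(on + off).

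| Share s | f, 7-year design | Ratio read | f, 5-year design | Ratio read |
|---|---|---|---|---|
| 10% | 0.10 | 1.90 | 0.05 | 1.95 |
| 30% | 0.24 | 1.76 | 0.14 | 1.86 |
| 50% | 0.35 | 1.65 | 0.21 | 1.79 |

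Reading 30% as a yearly probability (hazard -ln 0.70 = 0.357) lowers the bottom of the range slightly, to about 1.6.

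**5. Sensitivity to the abrupt end of risk.** Step 4 drops all excess on the day of stopping. If risk or detection carries over for 1 or 2 years, the 30% row moves from 1.76 to 1.82 or 1.88 (7-year design), and from 1.86 to 1.93 or 1.97 (5-year design).

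**The case against.** **The general rule that opens section 9.4 does stop at discontinuation.** It does, but the malignancy-specific text replaces it, and the 1/6 in the schematic shows that it does.

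**Latency work is left to the SAP.** Section 9.4 promises further analyses under different latency assumptions, and these may include an on-drug window. That stands as a possibility. It does not change the censoring rule the protocol already fixes, or the claim it already attaches to that rule.

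**Malignancy is expected to be delayed, and cited studies found similar rates on-drug and ever-exposed.** Both remarks support the primary analysis. The secondary is offered for the opposite assumption. By their titles, the cited studies concern TNF inhibitors and other biologics, not tofacitinib.

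**Stronger readings that a reader might infer, and that the documents do not support:**

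- *That the analysis cannot detect a promoter effect.* The excess keeps its direction. The claim of detection is too strong, but not wrong in sign.
- *That the protocol's own 30% implies a given dilution.* Taken as stated, all of those patients move to a bDMARD and are censored, so f would be 0 and the ratio would stay at 2.
- *That row 3, half off drug, means 2.0 becomes 1.5.* That applies a cohort formula to one illustrative patient whose on-drug years are inferred.
- *That censor-at-switch should be replaced.* A 90-day cut loses drug-promoted tumours diagnosed later, so the present analysis keeps a role.

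**The setting is modest.** This is a secondary analysis in a descriptive study with no hypotheses, and comparisons are made only if feasible. That limits the weight of the point but does not remove it.

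**Conclusion.** The point holds in limited form. Neither malignancy analysis specified in the protocol ends at discontinuation, and the one recommended for no or very short latency has a window that does not match that assumption. An effect present only on drug is attenuated toward no difference.

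The size cannot be taken from the documents. Under the assumed 30% yearly stopping, with 10% to 50% of stoppers starting no other class, a true ratio of 2 reads as about 1.95 to 1.65. It is closer to 2 if risk or diagnosis lags stopping. This takes bDMARDs to have no such effect themselves. Off-drug time is counted in that cohort too, so if they had one, both rates would be diluted. The remedy is cheap and uses data already held, so the change should be made, but the primary analysis does not depend on it.

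**What to change.** In section 9.4:

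1. Add an on-drug analysis for malignancy and NMSC, from the index date to 90 days after the end of treatment (the extension already used for other outcomes), with the same rule for tofacitinib and bDMARD. PML is already handled by pairing on-drug with ever-exposed.
2. Attach the no-latency or short-latency rationale to this analysis.
3. Keep censor-at-switch, and qualify its sentence to say that counted off-drug time dilutes an effect confined to treatment.
4. Editorial: the schematic note refers to another systemic therapy, while the censoring lists refer to an advanced one. Read literally, the note could end follow-up at a conventional DMARD. The legend suggests that advanced therapies are meant, so align the note with the lists.

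Cost: protocol and SAP wording, and one more run. The added analysis has fewer events and wider intervals, and misses some drug-promoted tumours diagnosed more than 90 days after stopping, which is why it should sit beside the existing two analyses.
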